9.7.2 Other Pharmacodynamic Variables

Numeric pharmacodynamic variables will be summarized using descriptive statistics for actual, CFB, and percent CFB values. Numeric variables include the following:

- MMT composite score – all muscle groups, upper extremity muscle groups, and lower extremity muscle groups

- Upper extremity muscle function using the Brooke scale
- Lower extremity muscle function using the Vignos scale
- INQoL domains and QoL score
- FSHD-HI: subscale and total scores (do not include the short form score)

Listings will be provided for all of the additional pharmacodynamic variables.

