4.2.3 Functional Assessment of Upper and Lower Limbs

Functional assessment of both the upper and lower extremities will be assessed at at Week 1, every 3 months (Week 12, 24, etc), and 1-Week Post-treatment Follow-up. Upper extremity muscle function will be measured using the Brooke scale. The grading for the Brooke scale is provided below:

Brooke Scale	Description
• 1	Starting with arms at the sides, the patient can abduct the arms in a full circle until they touch above the head
• 2	Can raise arms above head only by flexing the elbow (shortening the circumference of the movement) or using accessory muscles
• 3	Cannot raise hands above head, but can raise an 8-oz glass of water to the mouth
• 4	Can raise hands to the mouth, but cannot raise an 8-oz glass of water to the mouth
• 5	Cannot raise hands to the mouth, but can use hands to hold a pen or pick up pennies from the table
• 6	Cannot raise hands to the mouth and has no useful function of hands

Lower extremity muscle function will be measured using the Vignos scale. The grading for the Vignos scale is provided below:

Vignos Scale	Description
• 1	Walks and climbs stairs without assistance
• 2	Walks and climbs stair with aid of railing
• 3	Walks and climbs stairs slowly with aid of railing (over 25 seconds for eight standard steps)

- 4 Walks unassisted and rises from chair but cannot climb stairs
- 5 Walks unassisted but cannot rise from chair or climb stairs
- 6 Walks only with assistance or walks independently with long leg braces
- 7 Walks in long leg braces but requires assistance for balance
- 8 Stands in long leg braces but unable to walk even with assistance
- 9 Is in a wheelchair
- 10 Is confined to a bed

Scores for both the upper and lower extremity muscle function assessments will be considered as an ordinal variable.

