6.0 Definitions

Age

Age will be recorded on the CRF and not derived for this study.

Baseline

Baseline is defined as the baseline in the parent study.

Analyses of changes from pre-infusion to post-infusion (i.e., vital signs, and ECG) will use pre-infusion as well, when applicable. Post baseline values for tabulations will exclude unscheduled visit values; however, unscheduled visit values will be included in listings.

Change from Baseline

Change from baseline (CFB) will be calculated as (post-baseline – baseline). CFB will be calculated for patients with both a baseline and post-baseline value as applicable. Percent CFB will be calculated as (CFB/baseline)*100, where applicable.

If a baseline value has not been recorded for a parameter, then CFB will not be calculated for that parameter. Patients with missing CFB values will be excluded from analyses in which CFB is the endpoint.

Change from pre-infusion

Change from pre-infusion will be calculated as (post-infusion – pre-infusion). Change from pre-infusion will be calculated for patients with both pre-infusion and post-infusion values, as applicable. No imputation will be done for missing values.

Completion of study

A patient will be considered completed in the study when an End of Study CRF page indicates a completion date.

Concomitant medications

Concomitant medications are defined as any medications taken on or after the date of first date of infusion in the parent study. This includes medications that are ongoing at the time of first infusion.

Discontinuation of study

A patient will be considered discontinued from the study when an End of Study CRF page is completed indicating primary reason for discontinuation.

Prior medication

Prior medications are defined as any medications with start and stop dates prior to the date of first date of infusion in the parent study or an ongoing medications with a start date prior to first date of infusion in the parent study.

Protocol deviation

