9.0 Overall Statistical Considerations

All analyses will use SAS® version 9.4 or higher. Summary tables will be organized overall and by disease group, if applicable, for the two Safety populations. All available data will be used in the analyses, and important data will be included in data listings, sorted by site, patient and by visit within patient.

Unless otherwise noted, categorical data will be presented using counts and percentages, with the number of patients in the corresponding Safety population as the denominator for percentages. Percentages will be rounded to one decimal place except 100% will be displayed without any decimal places and percentages will not be displayed for zero counts. Continuous data, unless otherwise noted, are summarized using the number of observations (n), mean, standard deviation (SD), median, minimum, and maximum. Minimum and maximum will be rounded to the precision of the original value. Mean and median will be rounded to 1 decimal place greater than the precision of the original value. The SD will be rounded to 2 decimal places greater than the precision of the original value, up to a maximum of 3 decimal places. No statistical hypothesis testing will be performed for this study.

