14.3.2 Upper and Lower Extremity Muscle Function by Visit (Safety population Cumulative)

Disease Study Visit	Score = Brooke Scale								
	Actual			Change From Baseline			Percent Change from Baseline		
	N	Mean (SD)	Median (Min, Max)	N	Mean (SD)	Median (Min, Max)	N	Mean (SD)	Median (Min, Max)
Total (N = xx)									
Parent Study									
Baseline	xx	xx.x (xx.xx)	xx.x (xx, xx)						
Week 14/1-Week Follow-up	xx	xx.x (xx.xx)	xx.x (xx, xx)	xx	xx.x (xx.xx)	xx.x (xx, xx)	xx	xx.x (xx.xx)	xx.x (xx, xx)
Current Study (ATYR1940-C-006)									
Week 1	xx	xx.x (xx.xx)	xx.x (xx, xx)	xx	xx.x (xx.xx)	xx.x (xx, xx)	xx	xx.x (xx.xx)	xx.x (xx, xx)
Week 12	xx	xx.x (xx.xx)	xx.x (xx, xx)	xx	xx.x (xx.xx)	xx.x (xx, xx)	xx	xx.x (xx.xx)	xx.x (xx, xx)
...									
1-Week Post-treatment Follow-up	xx	xx.x (xx.xx)	xx.x (xx, xx)	xx	xx.x (xx.xx)	xx.x (xx, xx)	xx	xx.x (xx.xx)	xx.x (xx, xx)
<repeat for>									
EO-FSHD (N = xx)									
FSHD (N = xx)									
LGMD2B (N = xx)									

Note: FSHD=Facioscapulohumeral muscular dystrophy; LGMD2B=Limb-girdle muscular dystrophy 2B; EO-FSHD=Early Onset Facioscapulohumeral muscular dystrophy

Note: Baseline is defined as the baseline in the parent study.

Note: Brooke scale ranges from 1 to 6 with a lower actual score indicating a better response.

Note: Vignos scale ranges from 1 to 10 with a lower actual score indicating a better response.

Source: Listing xx.x.xx, Dataset: [NAME], Program: xxxxxx.sas, Output: T_14_3_2_XXXXX.rtf, Generated on: DDMMYYYY HH:MM

Page x of y

Programming Note: Include Brooke Scale and Vignos Scale. Assessments will be collected at Week 1, every months (Week 12, Week 24, etc), and 1-Week Post-treatment Follow-up.

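### Brooke and Vignos are declared ordinal but summarised as mean and percent change, and percent change is also applied to two signed INQoL treatment scores, where a negative baseline reverses its sign

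*SAP*

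**What the plan says.** SAP 4.2.3 states the measurement level of the two function scales: "Scores for both the upper and lower extremity muscle function assessments will be considered as an ordinal variable". SAP 9.7.2 then says: "Numeric pharmacodynamic variables will be summarized using descriptive statistics for actual, CFB, and percent CFB values". Its list of numeric variables includes "Upper extremity muscle function using the Brooke scale", "Lower extremity muscle function using the Vignos scale", "INQoL domains and QoL score" and the FSHD-HI scores.

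SAP 6.0 gives the formula: "Percent CFB will be calculated as (CFB/baseline)*100, where applicable". It sets no rule for a zero or negative baseline. SAP 9.0 supplies the default summary: "Continuous data, unless otherwise noted, are summarized using the number of observations (n), mean, standard deviation (SD), median, minimum, and maximum".

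The shells follow 9.7.2, not 4.2.3. Table 14.3.2 has mean (SD) and median (min, max) under actual, change and percent change. It contains no count per grade and no shift display. Table 14.3.3 uses the same layout for 15 INQoL scores, among them the Perceived and Expected Treatment scores. Table 14.3.4 does so for FSHD-HI.

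**The concern.** The ordinal declaration has no effect on the analysis. Percent change treats the grade number as a quantity with a true zero, but these scales start at 1 and the numbers are labels in order. The same one-grade step therefore gets a different percentage at each starting level, and averaging weights patients by where they began.

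The two INQoL treatment scores raise a separate problem. SAP 4.2.4 defines each as one item sum minus another, so the baseline can be negative. The percentage then has the opposite sign to the change it describes.

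Muscle function and quality of life are named parts of the exploratory activity objective (Protocol 3.1, SAP 2.0). With no control arm and no testing, these descriptive tables are the planned summary of those measures, so a misleading column matters even though no error rate is affected.

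**Working it through.** The SAP states no percent-change figure to reproduce, so the check applies its own formulas.

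**Inputs**
- Percent change P = 100 × (y1 − y0)/y0, with y0 the baseline (SAP 6.0).
- Direction and range for Brooke: "Note: Brooke scale ranges from 1 to 6 with a lower actual score indicating a better response". Vignos runs from 1 to 10, lower also better (Table 14.3.2).
- INQoL treatment scores: 100 × (A sum − B sum)/12, two items in each sum, each item on a seven-point scale (SAP 4.2.4).
- Up to 24 patients (SAP 3.2), in three disease groups in the shells.

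**1. Brooke and Vignos.** A one-grade worsening from grade g gives P = 100/g:

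| From grade | 1 | 2 | 3 | 4 | 5 | 9 (Vignos) |
|---|---|---|---|---|---|---|
| P | +100% | +50% | +33.3% | +25% | +20% | +11.1% |

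A one-grade improvement gives −100/g: −50% for 2 to 1, −16.7% for Brooke 6 to 5, −10% for Vignos 10 to 9.

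Take one patient going 1 to 2 and one going 2 to 1:
- Mean change = (+1 − 1)/2 = 0.
- Mean percent change = (+100 − 50)/2 = +25%.

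Because lower is better, the percent column reads as worsening in a pair with no net movement.

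The groups are small. Assuming an equal split of 24/3 = 8 per group, one patient going 1 to 2 moves the group mean by 100/8 = 12.5 percentage points. One going 5 to 6 moves it by 20/8 = 2.5. The documents do not give the actual split.

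**2. INQoL treatment scores.** With items coded 0 to 6, each two-item sum runs from 0 to 12, so the score runs from 100 × (0 − 12)/12 = −100 to +100. Coding 1 to 7 gives the same range. The 0 to 6 coding, with the first symptom item 1 to 7, also reproduces the SAP's other divisors: 7 + 6 + 6 = 19, 12×6 + 3×12 = 108, and 5×36 = 180.

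For y0 < 0, P has the opposite sign to y1 − y0:
- −25 to +25: change +50 points, P = 100 × 50/(−25) = −200%.
- −50 to −25: change +25 points, P = 100 × 25/(−50) = −50%.
- −25 to −50: change −25 points, P = 100 × (−25)/(−25) = +100%.

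Two patients who each rise 25 points (50 to 75, and −50 to −25) give P of +50% and −50%, a mean of 0%.

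Over all item combinations (0 to 6 coding), 45.2% give a negative score and 9.6% give zero. These are shares of possible responses, not expected patient frequencies.

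**3. Zero baselines.** The other 13 INQoL scores and FSHD-HI have a floor of 0. The INQoL scoring rules assign 0 in stated cases, and 0 on FSHD-HI means no disease burden (SAP 4.2.5). At y0 = 0, P is undefined. Just above 0 it is unstable: a symptom domain going from 1/19 (5.3) to 10/19 (52.6) gives +900%.

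**The case against.** The strongest reply is that percent change is one of three column blocks. In the two-patient Brooke example the adjacent absolute-change block shows mean 0, median 0, minimum −1 and maximum 1. In the treatment-score example it shows +50. Median with range already suits ordinal data, and patient-level values are listed, so other summaries can be rebuilt. There is no hypothesis testing, and Protocol 3.2.4 says that no specific quality-of-life endpoints have been defined. The documents give no baseline distributions, so how often zero or negative baselines will occur is unknown.

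All of that stands, and it limits the point to exploratory display. It also rules out several stronger readings that a reader might infer:
- That INQoL results generally reverse sign. Only 2 of the 15 scores can be negative, and Listing 16.2.21 shows percent change only for the overall QoL score, so for those two the reversal appears in Table 14.3.3 alone.
- That patients with least burden drop out of the analysis. They leave the percent block only, each block shows its own N, and the qualifier in SAP 6.0 can reasonably be read as excluding a zero denominator. For the treatment scores, zero means equal item sums, not low burden.
- That a move from −25 to +25 is an improvement. The SAP states a direction for the symptom and life domains but not for these two scores. The sign reversal holds whichever direction is better.

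The reply does not remove the contradiction between 4.2.3 and 9.7.2, nor the missing rule for negative baselines. A valid neighbouring column is no reason to print a wrong one.

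**Conclusion.** The point holds for the percent columns and for means of ordinal grades. For Brooke and Vignos, percent change for the same one-grade worsening varies fivefold (+100% to +20%) and ninefold (+100% to +11.1%) respectively, and can show +25% with no net movement. For the two INQoL treatment scores, every change from a negative baseline carries the wrong sign. For the other INQoL scores and FSHD-HI, the fault is limited to zero baselines.

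A reader might infer that the muscle-function and quality-of-life results as a whole are invalid. The documents do not support that: absolute change, medians and listings remain usable, the tables are descriptive, and the activity objective also draws on biomarkers, immune state, MRI and strength. The patient examples are constructed, so they show what the stated rules can produce, not how often.

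**What to change.** - **Brooke and Vignos:** take them out of the numeric list in SAP 9.7.2 so that it agrees with 4.2.3. Drop percent change. Add n (%) improved, unchanged or worsened from parent-study baseline by visit, as a shift or grade-count display, and keep median and range.
- **INQoL Perceived and Expected Treatment scores:** drop percent change, report absolute change in points, and state which direction is favourable.
- **Other INQoL scores and FSHD-HI:** make absolute change the summary. Either drop percent change, or state that it is not calculated when baseline is 0 and report how many patients are omitted.

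This touches Tables 14.3.2 to 14.3.4 and Listings 16.2.20 to 16.2.22. No new data are needed. The cost is SAP wording and some reprogramming, plus sparse cells with up to 24 patients over 6 or 10 grades and three disease groups; the improved/unchanged/worsened categories limit that. SAP 1.0 provides for a final version before database lock, and the document history labels version 2.0 a draft, so the change fits there.

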10.0 Validation

PRA's goal is to ensure that each TFL delivery is submitted to the highest level of quality. Our quality control procedures will be documented separately in the study specific quality control plan.

Appendix 1 Glossary of Abbreviations

Glossary of Abbreviations:	
Ab	Antibody
ADA	Anti-drug antibody
AE	Adverse event
ALT	Alanine aminotransferase
AST	Aspartate aminotransferase
ATC	Anatomic therapeutic classification
CDISC	Clinical Data Interchange Standards Consortium
CFB	Change from baseline
CK	Creatine kinase
CRF	Case report form
CS	Clinically significant
CSA	Cross sectional area
CTCAE	Common Terminology Criteria for Adverse Events
DLCO	Diffusion capacity of carbon monoxide
DMB	Data monitoring board
ECG	Electrocardiogram
EO-FSHD	Early onset Facioscapulohumeral muscular dystrophy
FEV₁	Forced expiratory volume in 1 second
FSHD	Facioscapulohumeral muscular dystrophy
FVC	Forced vital capacity
GGT	Gamma-glutamyl transferase
HARS	Human histidyl-tRNA synthetase
HLA	Human leukocyte antigen
INQoL	Individualized Neuromuscular Quality of Life
IRR	Infusion-related reaction
IV	Intravenous
LGMD2B	Limb-girdle muscular dystrophy Type 2B
MedDRA	Medical Dictionary for Regulatory Activities
MMT	Manual muscle testing
MRI	Magnetic resonance imaging
MSME	Multi-spin multi echo
NCS	Not clinically significant

OCT	Optical coherence tomography
PBMC	Peripheral blood mononuclear cell
PD	Pharmacodynamic
PFT	Pulmonary function test
PK	Pharmacokinetic
PT	Preferred term
QoL	Quality of Life
RBC	Red blood cell
SAE	Serious adverse event
SAP	Statistical analysis plan
SD	Standard deviation
SOC	System organ class
SpO₂	Oxygen saturation
STIR	Short tau inversion recovery
TEAE	Treatment-emergent adverse event
TFLs	Tables, figures, and listings
WBC	White blood cells
WHO DDE	World Health Organization Drug Dictionary Enhanced

Appendix 2 Adverse Event Start/Stop Date Imputation

Imputation Rules for Partial Dates (D = day, M = month, Y = year)

Parameter	Missing	Additional Conditions	Imputation
Start date for AEs	D	M and Y same as M and Y of first dose of ATYR1940	Date of first dose of ATYR1940 in current study.
		M and/or Y not same as date of first dose of ATYR1940	First day of month
	D and M	Y same as Y of first dose of ATYR1940	Date of first dose of ATYR1940 in the current study.
		Y prior to Y of first dose of ATYR1940 but same as Y of screening date	Date of screening date
	D, M, Y	None - date completely missing	Date of first dose of ATYR1940 in the current study.
Stop date for AEs	D	M and Y same as M and Y of 12-Week Follow-up visit	Date of 12-Week Follow-up visit
		M and/or Y not same as date of 12-week Follow-up visit	Use last day of month
	D and M	Y same as Y of 12-Week Follow-up visit	Date of 12-Week Follow-up visit
		Y not same as Y of 12-Week Follow-up visit	Use Dec 31
	D, M, Y	None - date completely missing	No imputation, but assume ongoing

Note: In all cases, if an estimated start date is after a complete stop date, use the first day of the stop date month.

Similarly, if the estimated stop date is before a complete or imputed start date, use the last day of the start day month.

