3.2 Sample Size Considerations

No formal sample size calculation was performed. Based on the design of the parent studies, it is estimated that up to 24 patients will be enrolled in this study.

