8.2 Missing Data Conventions

Rules for partial dates are provided in Appendices 2 and 3. These rules will apply to adverse events and medications. Missing values for other variables will not be imputed.

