14.2 SAFETY, TOLERABILITY, AND IMMUNOGENICITY DATA TABLES

14.2.1 ADVERSE EVENT DATA TABLES

14.2.1.1 Summary of Treatment-Emergent Adverse Events (Safety Population Cumulative)

	EO-FSHD (N = XX) n (%)	FSHD (N = XX) n (%)	LGMD2B (N = XX) n (%)	Total (N = XX) n (%)
Parent and Current Studies: Overall				
Number of TEAEs	xxx	xxx	xxx	xxx
Patients with any TEAE	xx (xx.x)	xx (xx.x)	xx (xx.x)	xx (xx.x)
Patients with any TEAE related ^a	xx (xx.x)	xx (xx.x)	xx (xx.x)	xx (xx.x)
Patients with any TEAE leading to study medication withdrawal	xx (xx.x)	xx (xx.x)	xx (xx.x)	xx (xx.x)
Patients with any serious TEAE	xx (xx.x)	xx (xx.x)	xx (xx.x)	xx (xx.x)
Patients with any TEAE with fatal outcome	xx (xx.x)	xx (xx.x)	xx (xx.x)	xx (xx.x)
Current Study (ATYR1940-C-006) Overall				
Number of TEAEs	xxx	xxx	xxx	xxx
Patients with any TEAE	xx (xx.x)	xx (xx.x)	xx (xx.x)	xx (xx.x)
Patients with any TEAE related ^a	xx (xx.x)	xx (xx.x)	xx (xx.x)	xx (xx.x)
Patients with any TEAE leading to study medication withdrawal	xx (xx.x)	xx (xx.x)	xx (xx.x)	xx (xx.x)
Patients with any serious TEAE	xx (xx.x)	xx (xx.x)	xx (xx.x)	xx (xx.x)
Patients with any TEAE with fatal outcome	xx (xx.x)	xx (xx.x)	xx (xx.x)	xx (xx.x)

Note: FSHD=Facioscapulohumeral muscular dystrophy; LGMD2B=Limb-girdle muscular dystrophy 2B; EO-FSHD=Early Onset Facioscapulohumeral muscular dystrophy

a. "Related" defined as possibly, likely, or definitely.

Note: Percentage based on the number of patients in the Safety population cumulative.

Source: Listing xx.x.xx, Dataset: [NAME], Program: xxxxxx.sas, Output: T_14_2_1_1_XXXXX.rtf, Generated on: DDMMYYYY HH:MM

Page x of y

14.2.1.2 Treatment-Emergent Adverse Events by System Organ Class and Preferred Term (Safety Population Cumulative)

	EO-FSHD (N = XX) n (%)	FSHD (N = XX) n (%)	LGMD2B (N = XX) n (%)	Total (N = XX) n (%)
Parent and Current Studies Overall				
Any treatment-emergent adverse event	xx (xx.x)	xx (xx.x)	xx (xx.x)	xx (xx.x)
System Organ Class 1	xx (xx.x)	xx (xx.x)	xx (xx.x)	xx (xx.x)
Preferred Term 1	xx (xx.x)	xx (xx.x)	xx (xx.x)	xx (xx.x)
Preferred Term 2	xx (xx.x)	xx (xx.x)	xx (xx.x)	xx (xx.x)
...				
System Organ Class 2	xx (xx.x)	xx (xx.x)	xx (xx.x)	xx (xx.x)
Preferred Term 1	xx (xx.x)	xx (xx.x)	xx (xx.x)	xx (xx.x)
Preferred Term 2	xx (xx.x)	xx (xx.x)	xx (xx.x)	xx (xx.x)
...				
System Organ Class 3	xx (xx.x)	xx (xx.x)	xx (xx.x)	xx (xx.x)
...				
Current Study (ATYR1940-C-006) Overall				

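### The adverse event date rules have no parent-study anchor, so parent-study events with partial start dates can be misplaced in the cumulative TEAE tables

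*SAP*

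**What the plan says.** SAP 8.2 sends partial dates to Appendices 2 and 3 and sets the scope without limit: "These rules will apply to adverse events and medications". Nothing restricts Appendix 2 to AEs with onset in 006.

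Parent-study AEs are in the analysis. SAP 5.2 builds the cumulative population from parent and 006 data. Table 14.2.1.1 has a block headed "Parent and Current Studies: Overall" and a separate 006 block, and Listing 16.2.9 takes AEs from both sources.

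For AE start dates, Appendix 2 works as follows.

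- Day missing, month and year matching the first dose: "Date of first dose of ATYR1940 in current study". Otherwise, the first of the month.
- Day and month missing, year matching the first dose: "Date of first dose of ATYR1940 in the current study".
- Day and month missing, "Y prior to Y of first dose of ATYR1940 but same as Y of screening date": the screening date.
- Everything missing: the first 006 dose.
- Override: "if an estimated start date is after a complete stop date, use the first day of the stop date month".

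The imputation cells name the current study. The condition cells say only first dose of ATYR1940. SAP Section 6 defines a TEAE for the current study only, as onset from the parent Week 13 visit (Week 13 Day 3 for study 004). For the pooled block the only definition is in protocol 9.2.9: onset after the first ATYR1940 dose, or an event present at baseline that worsens or is later judged drug-related.

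**The concern.** Elsewhere the SAP looks back to the parent study: baseline, and the split between prior and concomitant medication, are set from it. Appendix 2 does not. An AE from parent treatment with an incomplete start date is compared with, or assigned to, a dose given about three months after the patient's treatment began.

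Two kinds of error can follow. A parent event can appear as a 006 event, which inflates the 006 block. Or an on-treatment parent event can be dated before any dose and drop out of the TEAE counts, which is the non-conservative direction in a study whose first objective is safety. With few patients, single events are visible in the tables.

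**Working it through.** The plan has no figure to reproduce: "No statistical hypothesis testing will be performed for this study", and "No formal sample size calculation was performed". The check is to apply the rules literally.

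**Timeline.** The first parent dose is at parent Week 2 (SAP table programming notes) and the last at Week 13, 77 days later. The gap to the first 006 dose is ideally 1 week and at most 3 weeks unless an exception is agreed (SAP 3.1). First parent dose to first 006 dose is therefore 77 + 7 = 84 to 77 + 21 = 98 days. The 006 schedule has no screening visit, so the screening date is most naturally parent screening, before any dose.

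**Two illustrative patients** (dates invented), each with an on-treatment parent AE and no complete stop date:

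- P: screening 19 Sep 2016, first parent dose 17 Oct 2016, Week 13 on 2 Jan 2017, first 006 dose 9 Jan 2017, true onset 16 Nov 2016.
- Q: screening 4 Jul 2016, first parent dose 1 Aug, Week 13 on 17 Oct, first 006 dose 24 Oct, true onset 31 Aug 2016.

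| Patient, known part | Condition means first 006 dose | Condition means first-ever dose |
|---|---|---|
| P, month and year | 1 Nov 2016 | 1 Nov 2016 |
| P, year only | 19 Sep 2016, before any dose | 9 Jan 2017, a 006 TEAE |
| P, nothing | 9 Jan 2017, a 006 TEAE | 9 Jan 2017, a 006 TEAE |
| Q, month and year | 1 Aug 2016 | 24 Oct 2016, a 006 TEAE |
| Q, year only | 24 Oct 2016, a 006 TEAE | 24 Oct 2016, a 006 TEAE |
| Q, nothing | 24 Oct 2016, a 006 TEAE | 24 Oct 2016, a 006 TEAE |

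On the first-ever reading, two imputed dates contradict what is known (P's year, Q's month). That makes the 006 reading the more natural one, but the text does not settle it.

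**Effect of the override.** Give P a complete stop date of 26 Nov 2016. The undated event returns to 1 Nov 2016 on both readings. On the 006 reading the year-only event stays at 19 Sep 2016, because that date is already before the stop date.

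**First-of-month fallback.** Suppose P's AE began on 20 Oct 2016 with the day missing. The 006 reading gives 1 Oct 2016, 16 days before the first parent dose. The first-ever reading with a complete stop date of 26 Oct also gives 1 Oct, through the override.

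**How often, given a partial date.** Assume first-dose dates uniform over the year and onset uniform over the 77 days, so onset averages 38.5 days after the first parent dose.

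- A year boundary falls between the first parent and first 006 dose in 84/365.25 = 23% to 98/365.25 = 27% of patients.
- 006 reading, year-only, no complete stop date: the share sent to screening is (84 − 38.5)/365.25 = 12.5% to (98 − 38.5)/365.25 = 16.3%. The rest, about 84 to 88%, become 006 TEAEs. Simulation with screening 14, 28 or 42 days before the first parent dose gave the same ranges.
- Same reading, day missing: about 19% fall before the first dose and 2 to 11% become 006 TEAEs.
- Same reading, 7-day AE with a complete stop date: about 1% of year-only AEs become 006 TEAEs, but 21 to 25% still fall before the first dose.
- First-ever reading, no complete stop date: about 20% of day-missing and 90% of year-only AEs go to 006 Day 1. About 38.5/365.25 = 10.5% of year-only AEs have no rule (simulated 10.2 to 10.4%).

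**Weight of one patient.** 1/24 = 4.2 percentage points in the total column.

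**The case against.** A reader might infer that every rule uses the 006 dose and that every partially dated parent AE is certain to be misassigned. The documents do not support that. The first-of-month rows often leave a parent date in the right period. The override corrects nearly all false moves to 006 Day 1 when the stop date is complete. The condition column can be read as the first-ever dose, and the screening row then covers only AEs that truly precede treatment. A parent-recorded AE with onset after the Week 13 visit is already a 006 TEAE, so moving it to Day 1 changes nothing.

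A reader might also infer that a move to 006 Day 1 removes the event from the cumulative counts. It does not: an on-treatment parent AE remains a TEAE in the pooled block, and only the 006 block changes. Nor is a screening-dated event always lost, because the protocol definition retains baseline events that worsen or are later judged drug-related.

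The practical effect is probably small. Protocol 8.5.10.3 requires onset date and time, AEs are reviewed weekly on treatment, data are screened before lock, and Listing 16.2.9 shows actual dates, source study and TEAE flag. Parent AE dates may also arrive already imputed; the SAP does not say. All of this limits the size. None of it supplies a parent-dose anchor or settles which first dose the conditions mean.

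**Conclusion.** The point holds as a defect in a stated rule, at low severity. On either reading some parent-treatment AEs with incomplete start dates move to 006 Day 1, and a first-of-month or stop-month fallback can date an on-treatment AE before the first parent dose. Loss of a year-only event through the screening row occurs only if the condition means the first 006 dose and the screening date is parent screening. Its consequence for TEAE status rests on protocol 9.2.9, since the SAP gives no TEAE definition for the parent period.

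The percentages are conditional on an AE having a partial or missing start date and on the assumed date distributions; the documents do not say how many such AEs exist. The 4.2-point figure is a ceiling per patient in the total column at 24 patients, reached only if that patient has no other qualifying event in the row.

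Separately, a year-only AE in a year after the first-dose year has no rule although treatment is open-ended. Where that year also follows the first 006 dose, the AE is plainly post-dose, so this is a missing row rather than a lost TEAE.

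**What to change.** 1. Name the study in every condition cell of Appendix 2.
2. For the pooled block, set the imputed start to the later of the earliest date compatible with the known parts and the first parent-study dose, unless the known parts or a complete stop date show earlier onset. Delete the screening-date row for these AEs. Patient P's year-only event then starts on 17 Oct 2016 and counts as a pooled-block TEAE.
3. For the 006 block, do not default a parent-recorded AE to 006 Day 1. Count it only if its known parts place onset on or after the parent Week 13 visit. List separately those whose known parts and stop date allow onset on either side of that visit.
4. For year-only AEs in a year after the first-dose year, use 1 January of that year, as Appendix 3 does for medications.

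Anchoring purely by the study in which the AE was recorded would not be safe. Protocol 8.5.10.2 reports AEs through 30 days after the last parent dose in the parent study. With a 7-day gap that reaches 30 − 7 = 23 days into 006, so genuine 006-window events could be dropped. Step 3 guards against this.

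The cost is a rewrite of a few cells in Appendix 2, the matching derivation code and one short listing. No new data are needed.
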